9.3 Assessments of Adverse Events

Adverse events will be assessed for causality, seriousness and expectedness as described below.

9.3.1 *Seriousness assessment*

When an AE occurs, the investigator will confirm if the event is serious as per the definition given in section 9.1. If the self-reported adverse event details provided by the participant are not sufficient for the investigator to make an assessment, they will contact the participant for further information. If the event is classified as 'serious' then additional information may be requested to be completed by the participant to aid in the assessment of causality.

9.3.2 *Severity assessment*

The investigator will assess all SAEs for severity. Where possible the system used by CTCAE (Common Terminology Criteria for Adverse Events) v5.0 27-Nov-2017 should be used for event name and severity as outlined here:

Table 2: Severity Grade Definitions

GRADE 1 MILD	GRADE 2 MODERATE	GRADE 3 SEVERE	GRADE 4 POTENTIALLY LIFE THREATENING	GRADE 5 DEATH
Mild; asymptomatic or mild symptoms; clinical or diagnostic observations only	Moderate; minimal, local or noninvasive intervention indicated; limiting age appropriate instrumental ADL	Severe or medically significant but not immediately life-threatening; hospitalization or prolongation of hospitalization indicated; disabling; limiting self-care ADL	Life-threatening consequences; urgent intervention indicated	Death related to AE

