- Pre-existing disease or a condition present before treatment that does not worsen
- Hospitalization where no untoward or unintended response has occurred e.g. elective cosmetic surgery
- Overdose of medication without signs or symptoms

9.2 Procedures for recording and reporting of adverse events (AEs) and serious adverse events (SAEs)

Non-serious AEs as well as SAEs will be self-reported by the participant via online platform or SMS system. Participants are requested to provide details of any symptoms they have experienced and details of any hospitalizations. The investigator will be notified by the online system of all events self-reported by the participant in order to perform their assessment of the event and complete the 'Investigator Adverse Event Report. If the participant becomes very unwell, they will not be able to respond to the weekly SMS messages. As long as they have given consent for an alternative contact to be contacted (in line with local data protection requirements), the alternate contacts will be contacted. If the alternative contact confirms that the participant is unwell, or if they cannot be contacted, the site PI will be informed. The PI or delegate will investigate, assess the event and complete an AE form, called 'Investigator Adverse Event Report' on the online system, immediately and no later than within 24 hours if the event meets SAE criteria.

A notification will be also sent to the sponsor for all AEs meeting serious criteria, including those self-reported by the participant or assessed as SAEs by the PI or delegate. Treatment should be discontinued in line with Section 8.5. Automated reminders will be sent to participant or investigator if safety event related forms are not completed in the expected timelines.

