9.3.3 Causality assessment

The site investigator or delegated medically trained person, will assess the causality of all adverse events or reactions in relation to the IMP using the definitions in the table 3 below.

Once an AE is self-reported by a participant a notification will be sent to the site investigator or a delegated medically trained person. The causality assessment will be based on the information provided by the participant when the AE is reported. If this information is not sufficient to assess causality the assessor will contact the participant for further details to complete the process. If the assessor gets further relevant AE information from the participant that has not been added on the self-reported form, the assessor will provide new details on the online 'Investigator Adverse Event Report'.

Table 3: Causality Definitions

Category	Definition
Related	A causal relationship between an IMP/investigational treatment and an adverse event is at least a reasonable possibility , i.e., the relationship cannot be ruled out.
Not related	There is no reasonable possibility of a causal relationship between an IMP/investigational treatment and an adverse event.

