9.4 Notifications

The site Investigator or designee will receive an automated notification of the AE when it is initially self-reported by the participant. The investigator (or delegated medically trained person) must complete the causality and seriousness assessment. CCTU will receive notifications of all SAEs. Automated reminders will be sent to participant or investigator if safety event forms are not completed in the expected timelines. The site investigator will be notified of AEs via the electronic system, occurring from the time of randomization until 150 days after randomization. The Clinical Reviewer (medically qualified staff delegated by sponsor) will review all SAE reports received. In the event of disagreement between the causality assessment given by the investigator (or delegated medically trained person) and the Clinical Reviewer, both opinions and any justifications will be provided in subsequent reports. The Clinical Reviewer will review the assessment of expectedness based on possible wider knowledge of the reference material for the treatment. Country leads are responsible for the reporting of SUSARs to principal investigators and for ensuring reporting to relevant IRB/REC and national regulatory authorities as appropriate. Fatal and life threatening SUSARs must be reported to the regulatory authorities within 7 days of becoming aware of the event; other SUSARs must be reported within 15 days. Sponsor will keep country leads informed of any safety issues that arise during the course of the trial.

9.4.1 *Emergency Unblinding*

Every effort will be made to conceal the treatment allocation from participants and the trial teams. The trial code should only be broken for valid medical or safety reasons e.g. in the case of a severe adverse event where it is necessary for the investigator or treating health care professional to know which treatment the participant is receiving before the participant can be treated. Subject always to clinical need, where possible, members of the research team should remain blinded.

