11.1.2 Secondary outcomes

The following secondary outcome is of special interest: Severity of COVID-19 over the study period

- i) Uninfected – no clinical or virologic evidence of infection (Score = 0)
- ii) Ambulatory – no limitation of activities (score=1) or with limitation (Score=2)
- iii) Hospitalized – mild no oxygen (Score=3) or with oxygen (Score=4), hospitalized severe – Score=5-7*, dead (Score=8)

*Score 5 is non-invasive ventilation or high flow oxygen; Score 6 is intubation with mechanical ventilation; Score 7 is intubation with additional organ support (e.g. vasopressors, renal replacement therapy (RRT), extra corporeal membrane oxygenation [ECMO]).

These outcome definitions are based on WHO R&D Blueprint consensus definitions for COVID-19. The study period refers to the 60 days following commencement of trial intervention and an additional 3 months of observation period of participants i.e. 150 days in total. Moreover, severity will be reported based on a 60-day timeframe.

The secondary clinical outcomes consist of:

- Primary endpoint, but instead of the 60-day timeframe, over the course of the first 30 days after receiving trial interventions;
- Primary endpoint, but instead of the 60-day timeframe, over the course of the first 150 days after receiving trial interventions;
- Symptomatic COVID-19 (with subsequent virological confirmation) during the 150-day study period;
- Incident COVID-19 during the 60-day study period, which includes asymptomatic infections identified by serology samples taken at the time-point of study exit.

Table 4: Classification of Outcomes

Outcome	Baseline serology	60-day serology	150-day serology	RT PCR while symptomatic	COVID-19 symptoms
1. Nucleic acid confirmed COVID-19	+/-	+/-	+/-	+	+
2. Severe COVID-19	+/-	+/-	+/-	+	+ (scaled according to WHO ordinal severity scale)
3. Asymptomatic COVID-19	-	At least one of 2- or 5-month serology must be +	At least one of 2- or 5-month serology must be +	Not done	-
4. Presumed prior infection	+	+/-	+/-	- / not done	+/-
5. Other acute respiratory illness during trial	+/-	+/-	+/-	-	+

6. Symptomatic nucleic acid negative COVID-19; not primary outcome	-	At least one of 2- or 5-month serology must be +	At least one of 2- or 5-month serology must be +	-	+
--	---	--	--	---	---

Safety Outcomes

Safety outcomes will be determined according to the CTCAE (Common Terminology Criteria for Adverse Events) v5.0 27-Nov-2017 for grading severity of adult adverse events.

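### Safety outcomes rest on CTCAE grading of adverse events, but the core protocol instructs grading for SAEs and has no step that grades non-serious events

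*Combined protocol and SAP*

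**What the plan says.** The safety outcome is defined in one sentence at the end of section 11.1.2: "Safety outcomes will be determined according to the CTCAE (Common Terminology Criteria for Adverse Events) v5.0 27-Nov-2017 for grading severity of adult adverse events". It covers adverse events in general.

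Section 9 governs how events are captured and assessed:

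- **Capture (9.2).** "Non-serious AEs as well as SAEs will be self-reported by the participant via online platform or SMS system". The site is then brought in: "The investigator will be notified by the online system of all events self-reported by the participant", so that the investigator can assess the event and complete the Investigator Adverse Event Report.
- **General list of assessments (opening of 9.3).** "Adverse events will be assessed for causality, seriousness and expectedness as described below". Severity is not named.
- **Severity (9.3.2).** "The investigator will assess all SAEs for severity". Table 2 then sets out grades 1 to 5.
- **Causality (9.3.3).** The site investigator or a medically trained delegate "will assess the causality of all adverse events or reactions in relation to the IMP".
- **Notifications (9.4).** For a self-reported AE the investigator or delegate "must complete the causality and seriousness assessment". Severity is again not named.

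**The concern.** The outcome definition and the assessment procedure cover different sets of events. The outcome needs a severity grade for adverse events, while the grading instruction reaches serious ones. Non-serious events are collected and reviewed, but the variable that section 11.1.2 relies on is not requested for them.

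Severity and seriousness are different properties. A reaction can be unpleasant or temporarily limiting and still meet none of the seriousness criteria in Table 1. Participants enter without clinical evidence of COVID-19, and section 16 describes the study risks as low, so tolerability is a natural part of judging a preventive agent. Section 11.5 has the DMC weigh benefit against risk regularly. If non-serious events carry no grade, the DMC and the final report can see how many occurred in each arm, but not whether one arm's events were worse.

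The gap would be hard to close later. Grading afterwards from a participant's SMS or online text is less reliable than grading when the investigator is already looking at the event.

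**Working it through.** No formula applies. The point does not depend on sample size, power or an event rate, and the plan states no figure to reproduce. The check sets the sections side by side.

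| Element | Where | Scope as written |
|---|---|---|
| Safety outcome (CTCAE severity grade) | 11.1.2 | Adverse events, no restriction to serious |
| Collection | 9.2 | Non-serious and serious |
| Investigator notified and report completed | 9.2 | All self-reported events |
| Seriousness | 9.3.1 | Each AE |
| Causality | 9.3.3 | All adverse events or reactions |
| Expectedness | 9.3.4 | Events with possible involvement of the intervention |
| Severity grade | 9.3.2 | SAEs |

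**Step 1: what the outcome needs.** Section 11.1.2 calls for a CTCAE grade "for grading severity of adult adverse events", which includes non-serious ones.

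**Step 2: what the procedure yields for a non-serious event.** Sections 9.2, 9.3.1 and 9.3.3 yield its occurrence, a decision that it is not serious, and a judgement of related or not related. Section 9.3.4 adds expectedness where the intervention may be involved. No section asks the investigator, the participant or the sponsor's clinical reviewer for a grade.

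**Step 3: is the narrower scope of 9.3.2 deliberate?** The text says all SAEs, and it does not say that other events are excluded. The contrast with 9.3.3, which names all adverse events or reactions, favors reading the two scopes as different. Other features suggest a drafting slip. Table 2 defines grades 1 and 2, which suit few serious events. Section 9.3.4 treats a reaction as unexpected partly when it is worse than previously reported, and that judgement needs severity information for non-serious reactions too. The text does not settle which was meant.

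**Step 4: is grading supplied elsewhere?** Section 8.9 mentions grading tables, but as one basis for judging toxicity when IMP is stopped. It does not set up routine data capture for every event.

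**Step 5: which comparisons survive?** Counts of non-serious events, and counts of related ones, remain available by arm. Their distribution by grade does not. The loss concerns the separation of grade 1 from non-serious grades 2 and 3. Some grade 3 events will also be SAEs, because Table 2 places hospitalization and disabling events in grade 3 and Table 1 treats important medical events as serious. Grade 3 also covers limits on self-care, which need not meet any Table 1 criterion, so the overlap is not complete.

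**The case against.** The strongest reply is that the gap is inferred from silence. A reader might conclude that investigators grade serious events and nothing else, and that the safety outcome therefore cannot be produced for non-serious reactions. The documents do not support that conclusion. Section 9.3.2 sets a duty for SAEs and does not prohibit grading other events. The Investigator Adverse Event Report, the eCRF, the IMP appendices and the more detailed SAP announced in section 11.4 are not in the file, and any of them may carry a grade. The lists in 9.3 and 9.4 are weak evidence of exclusion, because they omit severity even for SAEs, where 9.3.2 plainly requires it. All of this stands. It limits the finding to what the core protocol instructs.

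A reader might also infer that a planned benefit-risk comparison by grade would be left incomplete. Section 11 specifies no such comparison, and the interim triggers in 11.5 rest on the odds ratio for efficacy. That stands too. What would be incomplete is the safety outcome stated in 11.1.2.

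Finally, grading SAEs alone could be a reasonable choice for a remote, pragmatic trial that may reach 30,000 participants and relies on self-report. If that is the choice, however, 11.1.2 does not reflect it. Reconciliation is needed either way.

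**Conclusion.** The mismatch is real and minor. Section 11.1.2 defines safety outcomes by severity grading of adverse events, and the core protocol contains no step that grades the non-serious ones. Followed as written, it would leave arms comparable on the count, seriousness and relatedness of those events but not on their severity.

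The affected class is the non-serious AEs in every arm. The documents give no adverse event rates, so the number of events and any effect on a comparison between arms cannot be estimated. The primary efficacy analysis and the sample size are unaffected.

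The conclusion rests on two assumptions: that sites follow section 9 as worded, and that no document outside the file already requires a grade. If one does, the data gap disappears and what remains is a correction to 9.3.2, 9.3 and 9.4 so that they match. It should not be read as showing that the outcome is unobtainable or that every non-serious event will in fact go ungraded.

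**What to change.** Preferred change, before data accrue:

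1. Reword 9.3.2 so that the investigator assesses severity for all AEs rather than all SAEs.
2. Add severity to the lists of assessments in 9.3 and 9.4.
3. Check that the Investigator Adverse Event Report has a CTCAE grade field, and add one if it does not.
4. State in section 11 that the highest grade per participant will be tabulated by arm.

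The investigator already reviews each self-reported event and completes a report on it, so the added work is modest site time per event. Some participants may have to be re-contacted when their self-report is too thin to grade.

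Alternative, if the sponsor intends SAE-only grading: leave 9.3.2 as it is and restate the safety outcome in 11.1.2 as graded SAEs plus ungraded counts of other AEs. This adds no site work, but it accepts that the severity of non-serious reactions will not be compared between arms.

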9.3.3 Causality assessment

The site investigator or delegated medically trained person, will assess the causality of all adverse events or reactions in relation to the IMP using the definitions in the table 3 below.

Once an AE is self-reported by a participant a notification will be sent to the site investigator or a delegated medically trained person. The causality assessment will be based on the information provided by the participant when the AE is reported. If this information is not sufficient to assess causality the assessor will contact the participant for further details to complete the process. If the assessor gets further relevant AE information from the participant that has not been added on the self-reported form, the assessor will provide new details on the online 'Investigator Adverse Event Report'.

Table 3: Causality Definitions

Category	Definition
Related	A causal relationship between an IMP/investigational treatment and an adverse event is at least a reasonable possibility , i.e., the relationship cannot be ruled out.
Not related	There is no reasonable possibility of a causal relationship between an IMP/investigational treatment and an adverse event.

9.3.4 Expectedness assessment

If there is at least a possible involvement of the trial interventions, the medically qualified staff delegated by sponsor must assess the expectedness of the event. An unexpected adverse reaction is one that is not reported in the current and approved version of the SPCs, or one that is more frequently reported or more severe than previously reported. See section 4.8 of the current and approved SPCs for a list of expected toxicities associated with IMPs used in this trial. If a SAR is assessed as being unexpected it becomes a SUSAR (suspected, unexpected, serious adverse reaction) and relevant Regulatory Authorities and Ethics Committees reporting guidelines apply.

9.4 Notifications

The site Investigator or designee will receive an automated notification of the AE when it is initially self-reported by the participant. The investigator (or delegated medically trained person) must complete the causality and seriousness assessment. CCTU will receive notifications of all SAEs. Automated reminders will be sent to participant or investigator if safety event forms are not completed in the expected timelines. The site investigator will be notified of AEs via the electronic system, occurring from the time of randomization until 150 days after randomization. The Clinical Reviewer (medically qualified staff delegated by sponsor) will review all SAE reports received. In the event of disagreement between the causality assessment given by the investigator (or delegated medically trained person) and the Clinical Reviewer, both opinions and any justifications will be provided in subsequent reports. The Clinical Reviewer will review the assessment of expectedness based on possible wider knowledge of the reference material for the treatment. Country leads are responsible for the reporting of SUSARs to principal investigators and for ensuring reporting to relevant IRB/REC and national regulatory authorities as appropriate. Fatal and life threatening SUSARs must be reported to the regulatory authorities within 7 days of becoming aware of the event; other SUSARs must be reported within 15 days. Sponsor will keep country leads informed of any safety issues that arise during the course of the trial.

9.4.1 *Emergency Unblinding*

Every effort will be made to conceal the treatment allocation from participants and the trial teams. The trial code should only be broken for valid medical or safety reasons e.g. in the case of a severe adverse event where it is necessary for the investigator or treating health care professional to know which treatment the participant is receiving before the participant can be treated. Subject always to clinical need, where possible, members of the research team should remain blinded.

If the person requiring the unblinded information is not the coordinating PI or national PI then that healthcare professional will contact the Investigating team to request the code break. Unblinding will take place if in the opinion of a treating physician a participant's health is compromised. The authorized individual will break the code and immediately inform the treating healthcare professional of the participant's treatment allocation. The treating physician has the ultimate decision and right to unblind the participant.

The code breaks for the trial are held on the online system and are the responsibility of the local site PI. The local site PI who will be authorized and delegated to perform code break by the national PI. If the person requiring the unblinded information is a member of the Investigating team then a request to the authorized individual to unblind will be made and the treatment allocation information obtained.

On receipt of the treatment allocation details the site PI or treating health care professional will treat the participant's medical emergency as appropriate. The site PI will document the breaking of the code and the reasons for doing so on the CRF and unblinding log and will file this in the site file. It will also be documented at the end of the trial in any final trial report and/or statistical report.

The Investigating team will notify the CCTU in writing as soon as possible following the code break detailing the necessity of the code break.

9.4.2 *Unblinding for the submission of SUSAR reports*

The following procedure will be used to unblind for the submission of a SUSAR report to the regulatory agencies. The Sponsor will be authorized to access the code break system for the purposes of unbinding for the submission of a SUSAR. On receipt of the treatment allocation, the Sponsor will

provide the unblinded SUSAR information to the relevant regulatory agencies. SUSAR reports will be disseminated to Investigators at site(s) and will remain blinded. The unblinded information will not be forwarded to the trial team and will be kept in a separated file with limited access.

9.5 Development Safety Update Reports

The sponsor will provide the main IRB/REC and relevant national drug regulatory agencies with Development Safety Update Reports (DSUR). The report will be submitted within 60 days of the Developmental International Birth Date (DIBD) of the trial each year until the trial is declared ended.

